#### 4.4 Statistical Design and Power

**Aim 1: Examine the feasibility, accessibility, acceptability, and responsiveness of a mHealth social norms intervention to improve AED adherence for adolescents with epilepsy.** H1: Adolescents with epilepsy will rate the intervention as highly feasible, easy to use, acceptable, and responsive to their needs.

*Analyses Aim 1: We will examine means and standard deviations of ratings completed by adolescents on the Adapted Feasibility and Acceptability Questionnaire, Revised Website/mHealth tool Evaluation Questionnaire (WEQ), and System Usability Scale. For the Adapted Feasibility and Acceptability Questionnaire, ratings of 3-4 are considered good. The WEQ is primarily qualitative in nature and will be used during Phase 1b modifications, as well as the RCT to obtain qualitative data on the use of the social norms mHealth tool. Finally, scores on the System Usability Scale ranging from 80-100 range indicate good to excellent usability.*

**Aim 2: Examine the preliminary efficacy of the mHealth social norms intervention on AED adherence, seizure severity, and HRQOL in adolescents with epilepsy.** H2a: Participants in the treatment group will demonstrate statistically significant *improvements* in adherence with corresponding medium/large effect sizes compared to the control group at post-treatment. H2b: Greater improvements in seizure severity, HRQOL, and adherence are expected at 3-month follow-up for the treatment versus control group.

*Analyses Aim 2: For the pilot RCT, adherence will be calculated using daily adherence data and collapsed for the one-month prior to treatment (baseline adherence) and the one-month following treatment (post adherence). For example, if a patient is prescribed their AED twice a day and takes 50 of their 60 doses in the month, their adherence rate would be 83.3% (total doses taken/total doses prescribed x 100%). For the follow-up period, three-month adherence will be calculated to assess sustainability of treatment effects. All analyses will be carried out with missing data assumed to be missing at random and handled via maximum likelihood estimation with auxiliary correlates within Mplus (Version 8) on the full randomized sample (N=80). An ANCOVA model will be used to test the primary hypothesis that the mHealth social norms group will demonstrate significantly higher adherence rates compared to the control group at post-treatment (one-month of adherence following intervention), after controlling for baseline adherence (1-month of adherence prior to intervention), age, sex, SES, seizure type, side effects, and cognitive/executive functioning (Aim 2, H2a). When examining our secondary outcomes (i.e., seizure severity, HRQOL) and adherence at 3-month follow-up (Aim 2, H2b), the same statistical model and covariate logic employed for our primary hypothesis will be used in a longitudinal mixed model.*

**Missing Data:** Strategies to minimize loss to follow-up are outlined in Form E: Section 2.5 Recruitment and Retention Plan. Data that remain missing despite our retention efforts will be accommodated in our analyses and their impact evaluated through sensitivity analyses. The models we propose can be estimated without bias under the missing at random (MAR) assumption and provide valid analysis as long as auxiliary covariates associated with missingness (if any) are included in the analysis model. To determine which covariates are associated with the missing data, we will create binary indicators of whether an observation was missing or not on each of the outcome variables, then use logistic regression to determine which covariates (if any) predict the “missingness” we observe on each of the outcomes. We can also examine whether those with complete data versus those with missing data differ on any of the outcomes.

**Power:** For the focus group and extended formative usage evaluation (ORBIT Phase 1a and 1b), we will use qualitative data analysis to modify the mHealth tools. A sample size of 10 for usability is sufficient to detect 95% of usability problems when pilot testing an mHealth tool.

Given timeline and resources proposed for this pilot RCT (ORBIT Phase II), we anticipate recruiting N=138 participants. We expect that 58% will have adherence  $\leq 95\%$ , leaving N=80 to be randomized. We conducted a Monte Carlo simulation in Mplus with N = 5000 replications, assuming a total randomized sample of N=80, 25% attrition, proper handling of missing data, standardization of all analysis variables, and that baseline adherence, age, sex, side effects, cognitive/executive functioning, seizure type, and SES (covariates) will explain at least 40% of the post-treatment adherence error variance (based on our pilot data and previous studies) Our analysis indicates that we will have at least 80% power to detect a post-treatment group difference effect size of  $d > 0.62$  in adherence rates (i.e., approximately 15% difference in group adherence

rates at post-treatment). Effect sizes for recently published social norms interventions have ranged from 0.41 to 0.85 when compared to those without social norms comparisons, and we have sufficient power to detect effects within the range of those published. The estimates of preliminary efficacy and variability of our social norms intervention that we obtain will be used to power for a future larger trial.

**Exploratory Analysis:** In this pilot trial, we plan to explore potential differences in treatment efficacy based on subgroups and other covariates. For example, we will examine whether our preliminary estimates of **efficacy vary as a function of sex, side effects, seizure type, cognitive/executive functioning, or age**. In our analyses, should we observe differences, we can use these variables as covariates in order to obtain unbiased and efficient estimates of our treatment effect. This information will also guide statistical power calculations and possible block randomization schemes for a future large-scale trial. We also plan to **explore potential mediators** of adherence change, including peer influence and adherence barriers, to better understand the full conceptual model that can be used to guide the design of a future full-scale trial. Finally, given that minimal clinically important differences in change for pediatric adherence have not been established, we will instead explore the clinical impact of our intervention by examining the **proportion of patients within each of our treatment groups who reach  $\geq 95\%$  adherence** at post-test and follow-up.

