After completion of the active intervention, automated digital reminders will be turned off, adherence feedback reports will cease to be sent, and social norms comparison will no longer be provided. Daily electronic adherence will be monitored until study completion. Additional questionnaires will be completed via REDCap or using paper/pencil questionnaires either in person or by mail at post-treatment (month 7), and 3-month follow- up (month 10).

**8.1 Data collection procedures and measures:** Participants will complete a demographic questionnaire that provides general information about the child's age, caregiver work history, family composition, socio-economic status, family history of seizures, history of seizures (e.g., type, who witness, when they occurred), and comorbid illnesses (e.g., learning disorders). In addition, caregivers and adolescents will complete the questionnaires detailed in the table below. An additional questionnaire related to the child's seizure severity (one item) will be obtained from the child's epilepsy provider. A medical chart review will also be conducted to describe key patient medical characteristics (e.g., epilepsy type and treatment, seizure frequency, quality of life, side effects, hospitalizations, emergency room visits, and telephone contacts to clinic staff between routine clinic visits). Chart reviews will cover the entire study period. See Table 2 for list. Due to the unexpected COVID-19 pandemic, we are also including a newly developed measure, the Impact of COVID-19 on Pediatric Epilepsy Management (ICPEM) to understand how COVID-19 is impacting our research participants and the outcomes of our study.

Raw adherence data will be obtained from the SimpleMed pillbox and AdhereTech bottles and will be used as the primary outcome variable. Data from these devices is obtained real-time via blue-tooth and 4G technology and thus will require no additional burden for participants. They will simply put their anti-seizure medicine in the electronic monitor (those who already use bottles will be given an AdhereTech bottle and those who use pillboxes will be given SimpleMed pillboxes). As highlighted on their companies' respective websites, the pillbox and bottles feature secure portals for the study team to access adherence data. In addition, the AdhereTech bottles feature a standard child-resistant caps. Instructions for using both devices will be provided to teens (see Appendix D).

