**Table 2. Questionnaires**

Questionnaire		# of items/Description/Score Used	Reliability/Validity
PRIMARY OUTCOME			
Adherence	SimpleMed+ Pillboxes	Daily objective adherence data; Score: % Adherence	N/A
	Self-Report Adherence 	1-item adherence item (caregiver and teen); Score: % Adherence	MEMS rho=0.46, p<.001
SECONDARY OUTCOMES			
Seizure Severity	Global Assessment of severity of epilepsy (GASE) 	1-item clinician report of seizure severity	Clinical vars: ( $r>.30$ ); ROC>.50
	Seizure Severity Scale-Adapted for children 	9-item caregiver report of seizure severity (e.g., intrusiveness, frequency, length, disruptiveness). Score: Total severity	$\alpha = 0.79$
Quality of Life	PedsQL Epilepsy Module 	29 items representing 5 domains of HRQOL (caregiver and teen); Scores: Impact, Cognitive, Sleep, Executive Functioning, and Mood/Behavior scales	$\alpha = 0.75-0.93$
COVARIATES			
Side effects	Pediatric Epilepsy Side Effects Questionnaire 	19 items assessing typical AED side effects (teen); Score: Total Side Effect Score	$\alpha = 0.72-0.93$
Demographics	Background Form	Child age, sex, and socioeconomic status (caregiver)	N/A
Medical variables	Medical Chart review	Seizure type, etiology, and treatment (e.g., AED)	N/A
COVID-19 Impact	Impact of COVID-19 on Pediatric Epilepsy Management (ICPEM)	25 item survey regarding personal/familial impact from COVID-19 Pandemic	N/A
MEDIATORS			
Peer Influence 	Resistance to Peer Influence Scale	10-item measure with paired statements that best describes situations related to peer influence (teen); Score: Total Score	$\alpha = 0.74$
Adherence Barriers	Pediatric Epilepsy Medication Self-Management Questionnaire 	27 items measuring medication self-management (teen and caregiver); Score: Barriers to Adherence Scale	$\alpha = 0.68-0.85$
TREATMENT FEASIBILITY/ACCEPTABILITY/USABILITY			
Usability	Revised Website/mHealth tool Evaluation Questionnaire (WEQ) 	8-item open-ended questions regarding the participant's general experience with the mHealth tool, expectations, comfort of use, quality of the tool, connectedness and likes/ dislikes (teen).	N/A
	System Usability Scale 	10-item scale that assessing the usability of an application or mHealth tool (adolescent)	N/A

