**Aim 2: Examine the preliminary efficacy of the mHealth social norms intervention on AED adherence, seizure severity, and HRQOL in adolescents with epilepsy.** H2a: Participants in the treatment group will demonstrate statistically significant *improvements* in adherence with corresponding medium/large effect sizes compared to the control group at post-treatment. H2b: Greater improvements in seizure severity, HRQOL, and adherence are expected at 3-month follow-up for the treatment versus control group.

*Analyses Aim 2: For the pilot RCT, adherence will be calculated using daily adherence data and collapsed for the one-month prior to treatment (baseline adherence) and the one-month following treatment (post adherence). For example, if a patient is prescribed their AED twice a day and takes 50 of their 60 doses in the month, their adherence rate would be 83.3% (total doses taken/total doses prescribed x 100%). For the follow-up period, three-month adherence will be calculated to assess sustainability of treatment effects. All analyses will be carried out with missing data assumed to be missing at random and handled via maximum likelihood estimation with auxiliary correlates within Mplus (Version 8) on the full randomized sample (N=80). An ANCOVA model will be used to test the primary hypothesis that the mHealth social norms group will demonstrate significantly higher adherence rates compared to the control group at post-treatment (one-month of adherence following intervention), after controlling for*

*baseline adherence (1-month of adherence prior to intervention), age, sex, SES, seizure type, side effects, and cognitive/executive functioning (Aim 2, H2a). When examining our secondary outcomes (i.e., seizure severity, HRQOL) and adherence at 3-month follow-up (Aim 2, H2b), the same statistical model and covariate logic employed for our primary hypothesis will be used in a longitudinal mixed model.*

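### The primary ANCOVA is fitted by maximum likelihood with no small-sample correction; with the usual large-sample test, a nominal 5% test has about 7.2% to 7.7% type I error

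*SAP*

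**What the plan says.** SAP 4.4 (Analyses Aim 2) sets the estimation method: "All analyses will be carried out with missing data assumed to be missing at random and handled via maximum likelihood estimation with auxiliary correlates". The software is Mplus 8 and the analysis set is all 80 randomised participants. Protocol section 8.3 says the same ("handled via maximum likelihood estimation with auxiliary correlates").

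The primary test follows directly: "An ANCOVA model will be used to test the primary hypothesis that the mHealth social norms group will demonstrate significantly higher adherence rates". The adjustment set is "baseline adherence (1-month of adherence prior to intervention), age, sex, SES, seizure type, side effects, and cognitive/executive functioning".

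The power paragraph, in SAP 4.4 and Protocol section 8.1 (sample size), rests on a simulation "assuming a total randomized sample of N=80, 25% attrition, proper handling of missing data". It takes the covariates to explain at least 40% of the outcome variance and claims 80% power or more at d = 0.62.

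Neither document states alpha, sidedness, the test statistic, its reference distribution, its degrees of freedom or any small-sample correction. The planned sensitivity analyses concern missing data, not the size of the test.

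**The concern.** Maximum likelihood estimates the residual variance as RSS/n. The unbiased estimate is RSS/(n − p), where p is the number of mean-model coefficients. The usual Wald test then uses a normal reference, and the likelihood-ratio test a chi-square reference. Both steps favour rejection. The effect is negligible when n is large relative to p, but here there may be about 60 outcomes and at least 9 coefficients.

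If that test is used, the primary p-value is too small and the confidence interval too narrow. The estimated arm effect is not biased. The residual variance is understated by 15% (51/60 = 0.85), and the plan intends to carry its variability estimates into the sizing of a larger trial.

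**Working it through.** **Inputs**
- Outcomes: 80 × 0.75 = 60 (power paragraph).
- Coefficients: intercept + arm + 7 covariates gives p = 9 if each covariate takes one column. Table 2 of the protocol scores the quality-of-life module as "Impact, Cognitive, Sleep, Executive Functioning, and Mood/Behavior scales"; entering the Cognitive and Executive scales separately gives p = 10. Reaching p = 12 needs further columns, such as a multi-category seizure type, and is an assumption.
- Alpha: not stated; two-sided 5% assumed. Allocation: 1:1 assumed.

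**The plan's own power figure.** With 30 per arm, residual SD √0.6 and d = 0.62, the noncentral t on 51 df gives 86.0% power. That formula assumes no chance correlation between arm and covariates. A simulation that allows for it (80 randomised, random 25% attrition, seven covariates, R² = 0.40, 40,000 trials) gives 80.9% for the t test and 86.0% for the uncorrected ML Wald test. Both satisfy the plan's claim, so the claim does not show which test was intended.

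**Size of the uncorrected tests.** Let t be the ordinary regression statistic for arm, on n − p df.
- Wald rejects when |t| > 1.96 × √((n − p)/n). For n = 60, p = 9: 1.96 × √(51/60) = 1.807, and 2·P(t₅₁ > 1.807) = 7.67%.
- Likelihood ratio rejects when n·log(1 + t²/(n − p)) > 3.841. For n = 60, p = 9 this is |t| > 1.836, giving 7.21%.
- The correct critical value on 51 df is 2.008.

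| Outcomes n | p | Wald | Likelihood ratio |
|---|---|---|---|
| 60 | 9 | 7.67% | 7.21% |
| 60 | 10 | 7.96% | 7.50% |
| 60 | 12 | 8.60% | 8.12% |
| 70 | 9 | 7.22% | 6.84% |
| 80 | 9 | 6.90% | 6.58% |
| 80 | 12 | 7.52% | 7.18% |

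A simulation of 100,000 null trials at n = 60, p = 9 gave Wald 7.6%, likelihood ratio 7.1% and t test 4.9%.

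**Consequences at n = 60, p = 9**
- Standard error: √(51/60) = 0.922 of its proper value, so 7.8% too small.
- Coverage of a 95% Wald interval: 100 − 7.67 = 92.3%.
- A t-test p of exactly 0.05 corresponds to z = 2.008 × √(60/51) = 2.178, an ML Wald p of 0.029. A reported ML p between 0.029 and 0.05 would therefore not be significant on the t test.

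**Closer to the trial's data**
- Outcome capped at 100 (20% to 34% at the cap; pre-cap SD 15/0.62 = 24.2; 40,000 trials): Wald 7.7%, likelihood ratio 7.2% to 7.3%, t test 5.0% to 5.1%.
- Capped outcome, one fully observed auxiliary driving missingness, 60 of 80 observed, 20,000 trials: Wald 7.4% to 7.7%; corrected as proposed below, 4.8% to 5.0%.

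**Which n to use.** If 80 is used in the correction when 60 are observed, the rejection limit is 1.994 × √((51/60) × (80/71)) = 1.951 on t₅₁, and size is 5.65%. Rescaling the variance correctly but keeping a normal reference leaves 2·P(t₅₁ > 1.96) = 5.55%. Both parts of the correction are needed.

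**The case against.** The strongest reply is that the plan is silent, not wrong. ANCOVA is conventionally tested with F or t on residual df, and on that reading size is 5%. This stands: the documents do not name a z or chi-square test. But they place this ANCOVA explicitly under maximum likelihood, and nothing in them points the analyst to a residual-df test.

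Other points have some force:
- **Sidedness.** H2a is directional. Under a two-sided 5% test, false claims of benefit occur in 3.8% of null trials (7.67/2) against 2.5% nominal. Under a one-sided 5% test, size would be 6.6% to 6.8%.
- **Attrition.** The 60 is a planning figure, and device data are passive: "Data from these devices is obtained real-time via blue-tooth and 4G technology and thus will require no additional burden for participants". More outcomes shrink the problem but do not remove it (6.6% to 6.9% at n = 80, p = 9).
- **The H2a decision.** H2a asks for significance together with a medium or large effect. If medium means d of at least 0.5 in raw SD units (an assumption), both conditions are met under the null in 2.3% of trials uncorrected and 2.2% corrected, counting either direction. The decision on H2a barely changes.
- **Pilot status.** The plan does not promise a confidence interval, and its efficacy aim is preliminary. It does, however, ask for statistical significance.
- **Limits of the check.** One fully observed auxiliary was simulated. Missing covariates were not, although several come from questionnaires.

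**Conclusion.** The concern holds, conditionally. If the primary arm effect is tested with the usual large-sample ML test at two-sided 5%, with 60 outcomes and 9 coefficients, type I error is 7.2% to 7.7%. More covariate columns raise it (8.1% to 8.6% at p = 12); fewer missing outcomes lower it. If the arm coefficient is instead referred to t on residual df with the unbiased variance, there is no inflation, but the plan does not say so.

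The harm is limited to the primary p-value and interval. The effect estimate is unaffected, and the joint H2a criterion hardly moves. It should be corrected before analysis because the choice of test can decide significance when the ML p-value lies between 0.029 and 0.05.

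**What to change.** Add two sentences to SAP 4.4 and mirror them in Protocol section 8.3:
1. State alpha and sidedness for the primary test.
2. Keep MAR, maximum likelihood and the auxiliaries, but multiply the estimated residual variance by n/(n − p) and refer the arm coefficient to t on n − p df. Define n as the number of participants with an observed post-treatment outcome, not the 80 randomised.

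Multiple imputation with least squares and Barnard-Rubin df is an alternative.

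Beyond the text, the cost is a short post-processing step and some apparent precision:

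| | p = 9 | p = 12 (assumed coding) |
|---|---|---|
| Confidence interval width | +11% | +15% |
| Power at d = 0.62 | 86% to 81% | 85% to 79% |
| d detectable with 80% power | 0.57 to 0.61 | 0.57 to 0.63 |

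These power figures use 30 per arm and allow for chance covariate imbalance; with perfect balance, power at p = 9 falls from 90% to 86%. At p = 12 power drops just under the plan's 80%, so fix the covariate columns first and then recheck the power statement.

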baseline adherence (i.e.,  $\geq 80\%$  or  $< 80\%$ ) and seizure severity (Global Assessment of Severity of Epilepsy; GASE scores 1-3 or 4-7). The PI will be blinded to study arm. The 80% criterion was selected based on our pilot data indicating that the median adherence rate for those randomized was 80%. Thus, the 95% adherence criterion is used to determine the eligibility of participants for randomization while the 80% criterion is used to balance intervention groups on baseline adherence within the randomization process. This randomization strategy will also minimize imbalance of the number of participants across groups. The randomization list will be held by an individual independent of the study to reduce any potential biases. Those who will be randomized will be notified of their randomization status within 48 hours. It is estimated that 58% of the sample will be eligible based on adherence  $\leq 95\%$  to be randomized to either the control group or intervention, yielding a final sample of  $n=80$ . Both groups will receive intervention for 5-months.

**8.3. Data Analysis:** All data analysis and management will occur at CCHMC. The Division of Behavioral Medicine and Clinical Psychology at CCHMC has developed a Divisional Data Core (DDC) in cooperation with the divisions of Biostatistics and Epidemiology and Bioinformatics to This group will provide quality reports to audit the data routinely, provide data for safety monitoring committee reports for the biostatisticians, and cleaning of the data.

**Aim 1: Examine the feasibility, accessibility, acceptability, and responsiveness of a mHealth social norms intervention to improve AED adherence for adolescents with epilepsy.** H1: Adolescents with epilepsy will rate the intervention as highly feasible, easy to use, acceptable, and responsive to their needs.

*Analyses Aim 1: We will examine means and standard deviations of ratings completed by adolescents on the Adapted Feasibility and Acceptability Questionnaire, Revised Website/mHealth tool Evaluation Questionnaire (WEQ), and System Usability Scale. For the Adapted Feasibility and Acceptability Questionnaire, ratings of 3-4 are considered good. The WEQ is primarily qualitative in nature and will be used during Phase 1b modifications, as well as the RCT to obtain qualitative data on the use of the social norms mHealth tool. Finally, scores on the System Usability Scale ranging from 80-100 range indicate good to excellent usability.*

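### GASE seizure severity is a randomisation stratum but not a covariate in the primary ANCOVA; adding it is a cheap, minor improvement

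*SAP*

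**What the plan says.** Protocol 8.1 (Randomization) uses permuted blocks of 2 or 4 within strata formed by two binary factors. For the first, "the 80% criterion is used to balance intervention groups on baseline adherence within the randomization process". The second is "seizure severity (Global Assessment of Severity of Epilepsy; GASE scores 1-3 or 4-7").

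The primary ANCOVA (SAP 4.4, Analyses Aim 2) compares the groups on post-treatment adherence after adjusting for "baseline adherence (1-month of adherence prior to intervention), age, sex, SES, seizure type, side effects, and cognitive/executive functioning". Protocol 8.3 gives the same list: baseline adherence plus "age, sex, SES, seizure type, side effects, and cognitive/executive functioning". The power simulation (SAP 4.4, Power) assumes those seven covariates, ending with "seizure type, and SES (covariates) will explain at least 40% of the post-treatment adherence error variance". Only baseline adherence is both a stratification factor and a covariate.

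For the secondary outcomes and follow-up adherence, "the same statistical model and covariate logic employed for our primary hypothesis will be used in a longitudinal mixed model". Missing data are "handled via maximum likelihood estimation with auxiliary correlates", and the Missing Data paragraph relies on the condition that "auxiliary covariates associated with missingness (if any) are included in the analysis model".

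Protocol Table 2 lists GASE as a one-item clinician rating among the secondary outcomes. Seizure type appears separately, as a chart-review covariate.

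**The concern.** An analysis should normally adjust for the factors used to balance the randomisation. Stratifying on a prognostic factor removes some chance variation from the treatment comparison. If the model leaves that factor out, its variance stays in the residual and the model standard error does not credit the balance the design has achieved.

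Nothing else in the plan supplies the adjustment. Seizure type is not severity. The missing-data paragraph would bring GASE in only if GASE were found to predict missingness. The auxiliary correlates are not named and serve missing data. The covariates named in the SAP's Exploratory Analysis do not include GASE either.

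At stake are a little precision and a standard error that matches the design. The second has some use beyond this test, because the SAP intends the estimates of efficacy and variability to inform the size of a larger trial.

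**Working it through.** **Inputs from the documents (SAP 4.4, Power).** 80 randomised; 25% attrition, so 80 × 0.75 = 60 analysed; seven covariates with R2 = 0.40; d = 0.62, equated to about 15 adherence points, so SD = 15/0.62 = 24.2 points.

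**Assumptions.** Two-sided alpha 0.05 (not stated). 1:1 allocation (implied by the block sizes). One term per covariate. Partial R2 of GASE beyond the seven covariates of 0, 0.02, 0.05 or 0.10. It is a share of the remaining 60% of variance, so 0.10 means 0.10 × 0.60 = 6% of the total.

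**1. Reproduce the stated power.** With p = 7 covariates and N = 60:

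- SE = sqrt(1 − 0.40) × sqrt(4/60) × sqrt(1 + 7/(60 − 7 − 3)) = 0.2135 SD
- noncentrality = 0.62/0.2135 = 2.90
- residual df = 60 − 2 − 7 = 51
- power from the noncentral t = 81.3%; d detectable with 80% power = 0.61

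This agrees with the plan's claim of at least 80% at d above 0.62. The claim does not depend on GASE.

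**2. Compare the models with and without GASE.** Simulation, two runs of 200,000 replications averaged: four strata (2 × 2), random blocks of 2 or 4, 25% random loss, GASE split 50/50, baseline adherence explaining 30% of variance and the other six covariates 10%. Both models are fitted by OLS to the same completers, with a t reference (df 51 without GASE, 50 with).

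| Partial R2 of GASE | 0 | 0.02 | 0.05 | 0.10 |
|---|---|---|---|---|
| True sampling SD, with/without GASE | 1.0037 | 1.0000 | 0.9939 | 0.9839 |
| OLS model SE, with/without GASE | 1.0035 | 0.9933 | 0.9778 | 0.9515 |
| Type I error without / with (%) | 5.0 / 5.0 | 4.8 / 5.0 | 4.6 / 5.0 | 4.3 / 4.9 |
| Power at d = 0.62 without / with (%) | 81.5 / 81.2 | 81.6 / 81.9 | 81.9 / 83.1 | 82.2 / 85.0 |
| Power change, type I error held at 5% (points) | −0.3 | −0.1 | +0.4 | +1.2 |

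The true SD breaks even at about 0.02; at 0.01 the ratio is 1.0020, so adding GASE is very slightly worse there. At 0.10 without GASE, a separate run gives a mean model SE of 0.212 against a true SD of 0.206: 0.212/0.206 = 1.029, an overstatement of roughly 3%. In adherence points, the 95% interval half-width without GASE is 2.008 × 0.212 × 24.2 = 10.3; with GASE it is 10.3, 10.2, 10.1 and 9.8 across the four columns. Bias without GASE was at most 0.006 SD in a 6,000-replication check.

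**3. Maximum likelihood with a normal reference.** The SAP specifies maximum likelihood but no reference distribution. The ML variance divides by n, so the SE shrinks by sqrt(51/60) = 0.922 without GASE and sqrt(50/60) = 0.913 with it. When GASE has no effect, the test rejects if |t| exceeds 1.96 × 0.922 = 1.807 on 51 df, about 7.7%, or 1.96 × 0.913 = 1.789 on 50 df, about 8.0%. Simulated type I error (completers, no auxiliary variables), without vs with GASE, is 7.7 vs 8.0, 7.4 vs 8.0, 7.2 vs 8.0 and 6.7 vs 7.9%.

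**4. Sensitivity (100,000 replications each).**

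- Four extra terms for multi-level covariates (df 47 to 46): OLS power goes from 78.0 to 77.7, 78.2 to 78.5, 78.5 to 79.8 and 78.7 to 81.7%. The drop below 80% comes from the extra terms.
- No attrition: true SD ratios 1.0008, 0.9999, 0.9983, 0.9938.
- GASE split 25/75: OLS power changes of −0.3, +0.3, +1.3 and +2.9 points.

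**The case against.** The strongest reply is that little precision is at stake. Stratification already balances GASE, so most of the benefit is in the planned estimate. At partial R2 0.10 the model SE falls by 4.9% but the true SD by only 1.6%; most of the 2.8-point power gain is recalibration of the standard error. This stands, and it is why the precision claim is limited to values above about 0.02. No document places GASE above or below that point.

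Second, under maximum likelihood with a normal reference, the extra term makes type I error slightly worse. This also stands, conditionally. It is a reason to fix the reference distribution and does not justify leaving a stratification factor out.

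Third, the simulation uses completers without auxiliary variables, so it is not exactly the planned analysis, and nothing was quantified for the follow-up or HRQOL models. Both are true limits on the figures.

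Fourth, the two factors may be treated differently for a reason: baseline adherence is the baseline of the primary outcome, whereas GASE measures a secondary one. That is plausible, but the documents do not say so. Nor does it prevent adjustment, since GASE must be known before randomisation.

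A reader might also infer that the omission biases the estimate, or that it undermines the 80% power. Neither follows: the estimate is unbiased either way, and the power reproduces without GASE. Nor can the planned test be called conservative. That holds under OLS with a t reference when GASE is prognostic, but reverses under maximum likelihood with a normal reference. Finally, the severity models cannot be said to lack baseline severity: the reused covariate logic plausibly includes it, but this is not stated.

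**Conclusion.** The mismatch is real: two stratification factors, of which one is in the model, with no reason given. Its effect is minor and depends on a quantity the documents do not give. Above a partial R2 of about 0.02, the OLS standard error overstates the sampling SD and a little precision is forgone. Even at 0.10, the largest value examined, the gain from adjusting is 1.2 points of power once type I error is held at 5%. Below about 0.02 no precision is gained.

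These sizes assume two-sided 5% testing, 60 completers lost at random and one term per covariate. The point is a cheap alignment of analysis with design, and the validity of the primary comparison is not in question.

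**What to change.** Add the GASE randomisation stratum (1-3 vs 4-7) to the covariates of the primary ANCOVA in SAP 4.4 and Protocol 8.3. By the same covariate logic, add it to the longitudinal models for follow-up adherence and HRQOL. State that the seizure-severity models include the baseline severity score. If the sponsor prefers to leave GASE out, a sentence giving the reason would close the documentation gap.

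The cost is one SAP line, no new data and one residual degree of freedom (51 to 50, or 47 to 46 with four extra covariate terms). If GASE has no prognostic value, about 0.3-0.4 points of power are lost. If the maximum-likelihood test would use a normal reference, type I error rises by about 0.3-1.2 points; specifying a t reference with residual degrees of freedom for the treatment test avoids this.
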